19. PHARMACODYNAMICS

[figure not shown]
CCI [Redacted]
[Redacted]
[Redacted]
[Redacted]

20. PLASMA ANTI-DRUG ANTIBODY TESTING

Absence (negative) or presence (positive) of ADA will be summarized and listed by treatment arm across all visits (refer to Section 3.2) based on the ADA analysis set. Positive ADA will be broken down further by neutralizing and non-neutralizing ADA.

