- h To be assessed only while hospitalized.
- i Includes oxygen requirement (ie, mode of delivery/liters of oxygen flow, FiO2 requirement), stop date of oxygen for patients who were discharged on home oxygen, extracorporeal membrane oxygenation support, noninvasive or invasive ventilator requirement, including start and stop of low- or high-flow oxygen supply or of any form of ventilation, and need for renal replacement therapy. Noninvasive ventilation refers to the delivery of mechanical ventilation to the lungs using techniques that do not require an endotracheal airway.
- j Only stop date of oxygen for patients who were discharged on home oxygen.
- k Information recorded is yes/no, hospitalization date, discharge date.
- l Laboratory tests performed within the 48 hours prior to enrolment will be accepted for determination of eligibility.
- m Hematology and clinical chemistry.
- n Hematology, clinical chemistry, liver function tests, cardiac panel, and coagulation.
- o Any laboratory tests performed as part of routine clinical care can be used for safety laboratory testing.
- p Hematology, clinical chemistry, and liver function tests.
- q If not done or entered into the eCRF within previous day.
- r Hematology, clinical chemistry, and liver function tests will be collected on the eCRF, if available, while the patient is in hospital.
- s This assessment will be performed on Day 15 or date of discharge, if earlier.

t *Samples for PK/PD assessments will be collected temporally as close as possible to Hour 0 (start of study drug infusion/dosing) within 60 minutes before the infusion as well as at the end of the infusion on Day 1 (within 30 minutes post infusion). If feasible, samples for PK and PD will be collected at Days 4, 7, 15, and 29 (or hospital discharge, if earlier) at any time during the day. Start and end of study drug infusion times (day, hour, minute) for each dose should be accurately recorded per 24-hour clock. All PK/PD sampling times (day, hour, minute) should be accurately recorded per 24-hour clock. No sample collection is required after discharge.* CCI

u *Antidrug antibody samples will be collected at Day 1 (pre-infusion within 30 minutes before the infusion) and at Days 15 and 29 (or hospital discharge, if earlier).*

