#### 4.1.1 Adverse Events

##### 4.1.1.1 Adverse Events from Approved Indications

The safety and tolerability of lanadelumab have been well characterized in HAE patients following SC administration.

Lanadelumab was approved by the US Food and Drug Administration on 23 August 2018 for prophylaxis to prevent attacks of HAE in patients aged 12 years and older. The safety, tolerability, efficacy and PK and PD results from these studies to date demonstrate that lanadelumab is safe and efficacious in HAE patients and have served as the basis of submissions for global expansion.

Per the reference labeling US Prescribing Information, the most common adverse reactions are injection site reactions, upper respiratory infections, headache, rash, myalgia, dizziness, and diarrhea. Other adverse reactions that occurred at a higher incidence in lanadelumab-treated patients compared to placebo include hypersensitivity, increased aspartate transaminase, and increased alanine transaminase.

Hypersensitivity is an important identified risk and is discussed in the warnings and precautions of the reference labelling. Immunogenicity and liver toxicity (European Union-specific) are important potential risks for lanadelumab and are monitored closely. Based on the review of the safety data from the completed and ongoing clinical trials, the known cumulative exposure and continuous pharmacovigilance monitoring for the risks, the benefit-risk continues to be favorable. Always refer to the latest version of the lanadelumab Investigator's Brochure for the overall benefit/risk assessment and the most accurate and current information regarding drug metabolism, PK, efficacy, and safety of lanadelumab.

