### 4.4 Plasma Anti-Drug Antibody Testing

Plasma samples for determination of the presence or absence of neutralizing or non-neutralizing ADA will be collected at Day 1 (pre-infusion) and at Days 15 and 29 (or hospital discharge, if earlier) (Section 1.2). Additional testing may be required in patients who have positive ADA. All sampling times (day, hour, minute) should be accurately recorded per 24-hour clock. Samples will be shipped to the study central laboratory and routed to a specialty laboratory for analysis.

CCI [REDACTED]

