3.2. SCHEDULE OF ACTIVITIES

The schedule of activities can be found in Section 1.2 of the sub-protocol COV-01-001.

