5.4. PLASMA ANTI-DRUG ANTIBODY ANALYSIS SET

The plasma anti-drug antibody (ADA) analysis set will include patients from the safety analysis set (refer to Master COV-01 SAP Section 5.2) randomized to COV-01-001 sub-protocol (i.e., Lanadelumab- IV + Standard of Care (SoC) arm or Placebo to Lanadelumab-IV + SoC) who have at least one evaluated ADA response.

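### The lanadelumab ADA summary defines no treatment-emergent category, so it does not separate antibodies already present before dosing from those that arise after it

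*SAP*

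**What the plan says.** Section 20 of the COV-01-001 SAP states: "Absence (negative) or presence (positive) of ADA will be summarized and listed by treatment arm across all visits". For visits it refers to section 3.2, which says: "The schedule of activities can be found in Section 1.2 of the sub-protocol COV-01-001". Footnote u of that schedule reads: "Antidrug antibody samples will be collected at Day 1 (pre-infusion within 30 minutes before the infusion) and at Days 15 and 29", or at hospital discharge if that comes first. Section 4.4 of the sub-protocol gives the same times.

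Section 20 provides one further split: "Positive ADA will be broken down further by neutralizing and non-neutralizing ADA". It makes no comparison with baseline and has no class for antibodies that are new or increased after dosing.

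The analysis set (SAP 5.4) is made up of treated patients randomized to this sub-protocol "who have at least one evaluated ADA response". It sets no condition on when that result was obtained.

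On the risk itself, sub-protocol section 4.1.1.1 says: "Immunogenicity and liver toxicity (European Union-specific) are important potential risks for lanadelumab".

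**The concern.** An immunogenicity summary is meant to show how often patients develop antibodies after receiving the drug. That needs a baseline status, a post-dose status and a rule linking the two. The trial collects both samples, but section 20 has no such rule.

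The sub-protocol names immunogenicity as a risk to be watched. It also says in section 2.2 that the intravenous route was not tested in the hereditary angioedema trials, and in section 4.1.1.2 it makes hypersensitivity an event of special interest. A reader of the report would take the ADA-positive figure as a rate on treatment. The planned figure could be too high, through antibodies present before dosing, or too low, through patients never sampled after dosing.

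**Working it through.** The documents state no ADA rate, so there is no figure to reproduce. The check sets the definitions side by side and then shows their effect with assumed counts.

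**Definitions compared**

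| Item | Where | Post-dose result required? | Baseline used? |
|---|---|---|---|
| ADA set and summary | COV-01-001 SAP 5.4, 20 | No | No |
| PK set | COV-01-001 SAP 5.2 | Yes | n/a |
| PD set | COV-01-001 SAP 5.3 | Yes | n/a |
| ADA summary | COV-01-005 SAP 20 | No, but an inconclusive class covers missing post-baseline results | Yes: induced, reduced, unaffected and boosted classes, plus totals for pre-existing and treatment-emergent ADA |

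**Arm size (assumption).** 29 patients were randomized to COV-01-001 (SAP 16). SAP 4.5.2 gives an imbalance of about 7:1 between active and control, but for the shared control arm under the Master SAP definition, which can hold placebo patients from other sub-protocols. If the ratio did apply within the 29, then 29 × 7/8 = 25.4, or about 25 active. If some controls came from elsewhere, the active arm is larger; 28 leaves one patient on lanadelumab placebo. I use 25 to 28. The ADA set takes only patients randomized to this sub-protocol, so its placebo arm would be 29 − 25 = 4 down to 29 − 28 = 1, too few to show background positivity.

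**Pooled reading.** Let N be active patients with a Day 1 result, b those positive only before dosing, m baseline-negative patients with no post-dose result, and t baseline-negative patients who become positive. All counts are assumed.

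- Planned rate = (b + t)/N
- Treatment-emergent rate = t/(N − m)
- Effect of one pre-existing positive on the planned rate: 1/25 = 4.0 points; 1/28 = 3.6 points

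| N | b | m | t | Planned | Treatment-emergent |
|---|---|---|---|---|---|
| 25 | 1 | 3 | 0 | 1/25 = 4.0% | 0/22 = 0% |
| 25 | 2 | 3 | 2 | 4/25 = 16.0% | 2/22 = 9.1% |
| 25 | 0 | 6 | 2 | 2/25 = 8.0% | 2/19 = 10.5% |
| 28 | 2 | 3 | 2 | 4/28 = 14.3% | 2/25 = 8.0% |

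The chance of at least one pre-existing positive is 1 − (1 − p)^N. For N = 25 it is 39.7%, 72.3% and 92.8% at p = 2%, 5% and 10%; for N = 28 it is 43.2%, 76.2% and 94.8%. The documents give no value for p.

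**By-visit reading.** Take N = 25 and m = 3, with all other 22 patients sampled at Day 15. Suppose the table shows 2/25 = 8.0% positive at Day 1 and 4/22 = 18.2% at Day 15. If the two Day 1 positives persist, two patients are treatment-emergent: 2/22 = 9.1%. If they turn negative, all four are: 4/22 = 18.2%. The same table fits both, so a by-visit table does not identify the treatment-emergent rate either.

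**The case against.** The strongest reply is that pooling is not stated. The phrase in section 20 also governs the listing, and a listing does not pool visits. It refers to the visit schedule, and the Master SAP (section 7) presents categorical data by arm and visit where applicable. A reader might infer that the plan fixes one ever-positive classification per patient; it does not say so. This stands, and the table shells that would settle it are not supplied. Pooling remains the more natural reading, because section 18 of the same SAP sets out PK visit by visit and timepoint by timepoint. The by-visit example above shows that the gap remains on the other reading.

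A reader might also infer that every patient without a post-dose sample is counted as negative. That is so only if the Day 1 sample was negative; if it was positive, pooling counts the patient as positive. Patients discharged early are due a sample at discharge, so baseline-only patients would arise mainly from early death, withdrawal or missed collection. Their number is unknown.

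Materiality is modest. Enrollment stopped early, the report is abbreviated, no efficacy inference is planned, ADA is not a primary or secondary endpoint, and no decision rule depends on the ADA rate. ADA results are also listed, ordered by patient and date, so a reader could find pre-dose positives by hand. That helps, but it leaves the definition to be chosen after the data are seen.

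Finally, the SAP rests on version 2.0 of the sub-protocol, while the text supplied is version 1.2 with part of its ADA section redacted. I assume the sampling times did not change. The missing category is a feature of the SAP itself.

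**Conclusion.** The point holds in a limited form. On either reading, the planned summary does not estimate treatment-emergent ADA. Under pooling, each pre-existing positive adds about 3.6 to 4 percentage points to the active-arm rate, and baseline-only negatives dilute it.

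The size rests on an assumed 25 to 28 active patients with an ADA result. The 7:1 ratio might be read as the split of the 29 randomized patients, but the SAP does not use it that way, so 25 is not established. The numbers of pre-existing positives and of patients without a post-dose sample are not given. The documents therefore do not support a claim that the reported rate will be wrong by a known amount or in a known direction.

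The change is worth making because it costs almost nothing and uses samples already scheduled. With a report this small and ADA results listed, it is not a threat to the trial's conclusions.

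**What to change.** In COV-01-001 SAP section 20, replace the single positive/negative summary with:

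- (a) Pre-infusion ADA prevalence, among patients with a baseline result.
- (b) Treatment-emergent ADA: baseline negative with at least one positive post-dose sample, among patients with a baseline result and at least one post-dose result. Give the neutralizing split here.
- Baseline-positive patients shown separately, with a boosted class as in COV-01-005 SAP section 20 if titers are available.
- Patients with no post-dose result shown as not evaluable.

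State how a post-dose positive without a baseline result is shown. Item (b) leaves such a patient out, whereas the COV-01-005 SAP counts the patient as treatment-induced. Also say whether any remaining visit table is per visit or pooled. Section 5.4 can keep its ADA set for (a) and the listing, with the post-dose condition added for (b).

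The cost is a smaller denominator for (b) and one reshaped table. No new samples are needed.

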21. DATA NOT SUMMARIZED OR PRESENTED

The list of data not summarized or presented is available in the Master COV-01 SAP.

APPENDIX 1 HYPERSENSITIVITY REACTIONS

Preferred Term

- Administration site hypersensitivity
 - Documented hypersensitivity to administered product
 - Drug hypersensitivity
 - Hypersensitivity
 - Infusion related hypersensitivity reaction
 - Infusion site hypersensitivity
 - Injection site hypersensitivity
 - Type I hypersensitivity
 - Type II hypersensitivity
 - Type IV hypersensitivity
-

APPENDIX 2 EVENTS OF DISORDERED COAGULATION

Preferred Term

[figure not shown]
- Abnormal clotting factor
- Acquired antithrombin III deficiency
- Acquired dysfibrinogenaemia
- Acquired factor IX deficiency
- Acquired factor VIII deficiency
- Acquired factor XI deficiency
- Acquired haemophilia
- Acquired protein S deficiency
- Acquired Von Willebrand's disease
- Activated protein C resistance
- Acute haemorrhagic oedema of infancy
- Anaphylactoid syndrome of pregnancy
- Antiphospholipid syndrome
- Antithrombin III deficiency
- Chronic pigmented purpura
- Coagulation disorder neonatal
- Coagulation factor deficiency
- Coagulation factor mutation
- Coagulopathy

CCI

PPD

Version Number: Amendment 3, v1.0
Version Date: 23-Jul-2021

[figure not shown]
CCI

Preferred Term

- Congenital coagulopathy
- Congenital dysfibrinogenaemia
- Congenital hypercoagulation
- Dilutional coagulopathy
- Disseminated intravascular coagulation
- Disseminated intravascular coagulation in newborn
- Ecchymosis
- Endothelial protein C receptor polymorphism
- Factor I deficiency
- Factor II deficiency
- Factor II inhibition
- Factor II mutation
- Factor III deficiency
- Factor IX deficiency
- Factor IX inhibition
- Factor V deficiency
- Factor V inhibition
- Factor V Leiden mutation
- Factor VII deficiency
- Factor VII inhibition

Preferred Term

- Factor VIII deficiency
- Factor VIII inhibition
- Factor X deficiency
- Factor X inhibition
- Factor XI deficiency
- Factor XII deficiency
- Factor XIII deficiency
- Factor XIII Inhibition
- Haemophilia
- Haemophilia A with anti factor VIII
- Haemophilia A without inhibitors
- Haemophilia B with anti factor IX
- Haemophilia B without inhibitors
- Haemophilic pseudotumour
- Haemorrhage
- Haemorrhagic diathesis
- Haemorrhagic disease of newborn
- Haemorrhagic disorder
- Haemorrhagic vasculitis
- Henoch-Schonlein purpura

[figure not shown]
CCI

PPD

Version Number: Amendment 3, v1.0
Version Date: 23-Jul-2021

CCI

Preferred Term

[figure not shown]
- Henoch-Schonlein purpura nephritis
- Heparin resistance
- Heparin-induced thrombocytopenia
- Hermansky-Pudlak syndrome
- Hypercoagulation
- Hyperfibrinogenaemia
- Hyperfibrinolysis
- Hyperhomocysteinaemia
- Hyperprothrombinaemia
- Hypersensitivity vasculitis
- Hyperthrombinaemia
- Hypocoagulable state
- Hypofibrinogenaemia
- Hypoprothrombinaemia
- Hypothrombinaemia
- Hypothromboplastinaemia
- Increased tendency to bruise
- Infantile scurvy
- Methylenetetrahydrofolate reductase deficiency

1. INTRODUCTION

This statistical analysis plan (SAP) describes the rules and conventions to be used in the presentation and analysis of data specific to sub-protocol COV-01-004 of master protocol COV-01. It describes the specific data to be summarized and analyzed, including specifics of the statistical analyses to be performed.

This sub-protocol SAP is based on version 4.0 of the sub-protocol COV-01-004, dated 14Apr2021.

For the rules and conventions to be used in the presentation and analysis of data common across all sub-protocols, refer to the Master COV-01 SAP.

2. STUDY OBJECTIVES

The study objectives are described in the Master COV-01 SAP.

3. STUDY DESIGN

3.1. GENERAL DESCRIPTION

[figure not shown]
The general description is available in the Master COV-01 SAP.

3.2. SCHEDULE OF ACTIVITIES

The schedule of activities can be found in Section 1.2 of the sub-protocol COV-01-004.

3.3. CHANGES TO PLANNED ANALYSES FROM MASTER PROTOCOL COV-01 AND SUB-PROTOCOL COV-01-004

There are no changes to the analyses planned for master protocol COV-01 and sub-protocol COV-01-004.

4. PLANNED ANALYSES

The planned analyses are listed and described in the Master COV-01 SAP.

All outputs described in this sub-protocol SAP will be produced at the time of sub-protocol COV-01-004 primary analysis (refer to COV-01 Master SAP).

In addition to the outputs planned to be produced at the time of COV-01-004 sub-protocol final analysis (refer to COV-01 Master SAP), safety outputs described in this sub-protocol SAP will also be produced at the time of COV-01-004 sub-protocol final analysis (refer to Section 17.1).

5. ANALYSIS SETS

Analysis sets are described in the Master COV-01 SAP.

An additional analysis set that is specific to sub-protocol COV-01-004 is described below:

5.1. PHARMACOKINETIC ANALYSIS SET

The pharmacokinetic (PK) analysis set will include all patients included in the safety analysis set (refer to Master COV-01 SAP Section 5.2) who were randomized to the apremilast plus Standard of Care (SoC) treatment group and have at least one measured PK concentration.

[figure not shown]
5.2. PHARMACODYNAMIC ANALYSIS SET

The pharmacodynamic (PD) analysis set will include all patients included in the safety analysis set (refer to Master COV-01 SAP Section 5.2) who were randomized to the COV-01-004 sub-protocol (i.e., apremilast plus SoC or placebo to apremilast + SoC treatment groups) and have at least one measured post-baseline biomarker level.

5.3. PROCESS FOR ANALYSIS SET ASSIGNMENT

As the PK analysis set is defined based on objective criteria only, the authorization of this sub-protocol SAP will stand for the agreement and authorization of the inclusion/exclusion of each patient in this PK analysis set.

CCI	[Redacted]		
PPD	[Redacted]	Version Number:	Amendment 1, v1.0
		Version Date:	23Apr2021
CCI	[Redacted]	[Redacted]	[Redacted]
	[Redacted]		
	[Redacted]		
	[Redacted]		

6. GENERAL CONSIDERATIONS

Details are provided in the Master COV-01 SAP.

7. STATISTICAL CONSIDERATIONS

7.1. SAMPLE SIZE CALCULATION

Details are defined in the Master COV-01 SAP.

7.2. MISSING DATA

Details are defined in the Master COV-01 SAP.

7.3. STATISTICAL TESTS

Details are defined in the Master COV-01 SAP.

7.4. MULTIPLE COMPARISONS/MULTIPLICITY

Details are defined in the Master COV-01 SAP.

7.5. MULTICENTER STUDY

Details are defined in the Master COV-01 SAP.

7.6. ADJUSTMENTS FOR COVARIATES AND FACTORS TO BE INCLUDED IN ANALYSES

Details are defined in the Master COV-01 SAP.

7.7. EXAMINATION OF SUBGROUPS

For sub-protocol COV-01-004, additional subgroup analyses will be performed for selected safety data (refer to Section 17.1). The additional subgroup is:

- Patients randomized to sub-protocol COV-01-004 (apremilast plus SoC and placebo plus SoC treatment groups) plus patients included in COV-01-004 control arm (refer to Master COV-01 SAP Section 4.5) that have been randomized to the placebo plus SoC treatment group of a sub-protocol other than COV-01-004 and who did not receive any concomitant dose of apremilast during the course of the study (refer to Master COV-01 SAP Section 14 for concomitant use definition). That is, placebo plus SoC patients included in the control arm of COV-01-004 who were randomized to a sub-protocol other than COV-01-004 and who concomitantly took apremilast during the course of the study will be excluded from this subgroup.

It is to be noted that these subgroup analyses will be performed only if more than 10% of patients included in COV-01-004 control arm, that have been randomized to a sub-protocol other than COV-01-004, concomitantly took apremilast during the course of the study.

7.8. SOFTWARE VERSION

Details are defined in the Master COV-01 SAP.

8. OUTPUT PRESENTATIONS

Output presentations are described in the Master COV-01 SAP.

9. DISPOSITION AND WITHDRAWALS

Analysis of disposition and withdrawals is described in the Master COV-01 SAP.

10. DEMOGRAPHIC AND OTHER BASELINE CHARACTERISTICS

Analysis of demographic and other baseline characteristics is described in the Master COV-01 SAP.

CCI [Redacted]

11. DISEASE HISTORY

Analysis of disease history at screening is described in the Master COV-01 SAP.

12. MEDICAL HISTORY

Analysis of medical history is described in the Master COV-01 SAP.

13. PRIOR AND CONCOMITANT MEDICATIONS

Analysis of prior and concomitant medications is described in the Master COV-01 SAP.

14. EXPOSURE TO STUDY DRUG

Patients randomized to sub-protocol COV-01-004

Patients randomized to the apremilast plus SoC or placebo plus SoC treatment groups of COV-01-004 sub-protocol will receive either an apremilast 30 mg or matching placebo tablet, as applicable, twice daily (BID) in a double-blind manner for 14 days or until hospital discharge, death, or discontinuation of study drug, whichever occurs first, in addition to SoC.

Reason for dose modification of study drug (i.e., dose increased, dose reduced, drug interrupted, drug withdrawal, and unknown) will be captured on the *Exposure* page of the electronic Case Report Form (eCRF).

Patients included in the control arm of COV-01-004 sub-protocol who were randomized to the placebo plus SoC group of a sub-protocol other than COV-01-004

It is to be noted that the planned duration of exposure to a study drug, planned frequency of administration of the study drug, and planned route of administration of the study drug will vary from one sub-protocol to the other, but similar information as for COV-01-004 sub-protocol will be captured on the *Exposure* page of the eCRF of these other sub-protocols.

[figure not shown]
CCI [Redacted]

PPD [Redacted]

Version Number: Amendment 1, v1.0
Version Date: 23Apr2021

CCI [Redacted]

[figure not shown]
[Redacted]

Exposure to study drug

The exposure to study drug will be summarized by treatment arm (breaking down the placebo plus SoC arm by sub-protocol) based on the safety analysis set as follows:

- Duration of exposure:
 - Duration of exposure (days) as a continuous variable;
 - Duration of exposure (days) as a categorical variable: 1 to 3, > 3 to 7, > 7 to 14, and > 14;
 - Total number of doses received as a continuous variable, where the total number of doses received is defined as the total number of doses received by each patient, not the total number of doses received across all patients.
- Average dose (mg/day) only for patients randomized to sub-protocol COV-01-004;
- Dose modifications:
 - Number and percentage of patients with at least one dose reduction;
 - Number and percentage of patients with a dose reduction by reason for dose reductions:
 - Adverse events;
 - Due to creatinine clearance < 30 mL/min*;
 - Due to renal replacement therapy*;
 - Other.
 - Total number of dose reductions as a continuous variable, where the total number of dose reductions defined similarly to the total number of doses received;
 - Among patients with a dose reduction, number and percentage of patients with dose subsequently increased back to the planned dose level;
 - Number and percentage of patients with at least one interrupted dose;

- Number and percentage of patients with at least one dose interruption by reason for dose interruption:
 - Adverse events;
 - Due to creatinine clearance < 30 mL/min*;
 - Due to renal replacement therapy*;
 - Other.
- Total number of dose interruptions as a continuous variable, where the total number of dose interruptions is defined similarly to the total number of doses received;
- Among patients with a dose interruption, number and percentage of patients with dose subsequently restarted at planned dose level;
- Number and percentage of patients with at least one overdose.

* Applicable only for patients randomized to sub-protocol COV-01-004.

All dosing and exposure data will also be listed.

